# 7.6. Medical History and Medical Conditions Present at Entry

Past or current relevant medical history information will be summarized and listed.

# 7.7. Prior and Concomitant Non-HAE and HAE Medications

Medication use is collected for the period from 30 days prior to Screening to study completion, except for contraceptives which are collected from 60 days prior. Medications collected in the eCRF that were received and stopped prior to the date of first dose will be considered prior medications. Medications will be considered as concomitant if the start date of the medication is

on or after the date of first intake of study drug or if the start date is prior to the first date of study drug but the medication is ongoing during the treatment period in the study. Medications taken at any time during Part 1 of the study will be considered with Part 1 treatment. Similarly, medications taken at any time during Part 2 or 3 of the study will be considered with Part 2 treatment. For example, a medication which is started during Part 1 while a subject is assigned to a Part 1 treatment of placebo will appear in the Part 1 only summary under the placebo column. If that treatment is continued into Part 2 where the subjects is assigned to a treatment of 110 mg, the medication will also be summarized in the treatment column labeled "110 mg after placebo" in the summary of concomitant medications for the entire study period.

Medication verbatim text will be coded using the WHO Drug Dictionary, March 2017. A summary by Part 1 treatment of recently discontinued medications taken within 30 days of screening but discontinued prior to dosing will be provided.

Separate summaries of concomitant medications for Part 1 only and for the entire study period will be presented using the treatment descriptors in Table 5 and Table 7, respectively. The number and percentages of subjects taking each medication will be summarized by WHO preferred name. Multiple uses of the same medication (by preferred name) will be counted once only per subject per study treatment. No inferential statistics will be provided.

HAE-related medications will be similarly summarized for Part 1 only and for the entire study period.

An attack-level summary will also be provided showing the number of attacks for which the various HAE-related medications were taken based on the subject diary and the concomitant medication form (androgens) in the eCRF.

All medication data will be listed.

# 7.8. Baseline Physical Examination

Physical examination data will be listed.

# 7.9. Baseline Primary and Secondary Efficacy Evaluations

All attacks will be listed. The baseline attack rate and the categorized baseline attack rate will be summarized by Part 1 treatment using descriptive statistics for baseline attack rate and n [%] for the categorized baseline attack rate. The proportion of days with HAE symptoms will also be included in the summary.

Similarly, a summary of baseline of AE-QoL total and domain scores will be provided by Part 1 treatment.

# 8. EFFICACY

# 8.1. General Considerations

Data from all centers will be combined for analysis.

Hypothesis tests will be 2-sided. Hypotheses comparing each of the 2 active dose groups to placebo will be separately tested. Analyses of Part 2 data will be descriptive. No hypotheses will

be tested for Parts 2 and 3 nor will hypothesis testing be conducted to compare the 2 active dose groups.

## 8.2. Testing Statistical Assumptions Including Comparability at Baseline

A summary of subgroups will be provided by Part 1 treatment. In addition, the duration of baseline period, baseline attack rate, categorized baseline attack rate ( $\geq 2$  attacks/month vs. < 2 attacks/month), and baseline AE-QoL will be summarized by Part 1 treatment.

## 8.3. Statement of the Null and Alternate Hypotheses

Hypothesis testing will be conducted for Part 1 only. The primary null and alternative hypotheses, for each active dose separately, are:

- Ho: RA = RP; active treatment does not have a differential effect on the rate of investigator-confirmed HAE attacks
- $H_A: R_A \neq R_P$ ; active treatment does have a differential effect on the rate of investigator-confirmed HAE attacks

where  $R_A$  is the monthly attack rate for active treatment and  $R_P$  is the monthly attack rate for placebo treatment.

Secondary hypotheses are (in order of hierarchical testing):

- 1. AE-QoL
  - $H_0: \beta = 0$ ; active treatment does not have a differential effect on the change from baseline AE-QoL at Week 24
  - $H_A: \beta \neq 0$ ; active treatment does have a differential effect on the change from baseline AE-QoL at Week 24

where  $\beta$  is the parameter representing treatment effect for the dose of interest in a mixed-effects model with repeated measures (MMRM).

- 2. Proportion of days with angioedema symptoms
  - Ho:  $\beta = 0$ ; active treatment does not have a differential effect on the proportion of days with angioedema symptoms over the entire treatment period
  - HA:  $\beta \neq 0$ ; active treatment does have a differential effect on the proportion of days with angioedema symptoms over the entire treatment period

where  $\beta$  is the parameter representing treatment effect for the dose of interest in an analysis of covariance (ANCOVA) model.

- 3. Rate of investigator-confirmed HAE attacks during the effective treatment period (beginning on Day 8 through 24 weeks)
  - Ho: RA = RP; active treatment does not have a differential effect on the rate of investigator-confirmed HAE attacks during the effective treatment period
  - $H_A: R_A \neq R_P$ ; active treatment does have a differential effect on the rate of investigator-confirmed HAE attacks during the effective treatment period

where  $R_A$  is the monthly attack rate for active treatment and  $R_P$  is the monthly attack rate for placebo treatment during the effective treatment period.

## 8.4. Subgroup Analyses

Subgroup analyses for the primary endpoint of investigator-confirmed attack rate during the entire 24-week dosing period and the secondary endpoint of Week 24 change from baseline AE-QoL (total score) will be provided by:

- 1. Region (North America vs. Europe)
- 2. Sex
- 3. Race (white vs. other)
- 4. Baseline attack rate ( $\geq 2$  attacks/month vs. < 2 attacks/month)
- 5. Age group (< 18, 18 to 65, > 65 years)

Forest plots showing the original results and the results by subgroups will be provided.

A summary of TEAEs by age group will also be provided.

## 8.5. Multiple Comparisons and Multiplicity

There are 4 endpoints being tested. For each endpoint, there are 2 potential doses to be tested against placebo. The Type I error rate will be controlled at the study level by using a combination of hierarchical testing and the Hochberg procedure. The 4 endpoints will be tested in a hierarchical fashion, and the 2 doses will be tested using the Hochberg step-up procedure at each level of the hierarchy to which both doses progress through the hierarchy.

The first endpoint to be tested is the primary endpoint, the rate of investigator-confirmed HAE attacks during dosing in the entire 24-week treatment period of Part 1. Using the Hochberg step-up procedure, each of the 2 doses will be tested at the  $\alpha = 0.05$  level, comparing active treatment to placebo. If the maximum of the 2 p-values is < 0.05, the null hypotheses of no difference between the rate of attacks for subjects on active and placebo treatment will be rejected for both doses and testing will proceed to the next endpoint in the hierarchy with  $\alpha = 0.05$ . If the maximum of the 2 p-values is > 0.05 but the minimum of the 2 p-values is < 0.025, the null hypothesis for the dose with p < 0.025 will be rejected and testing for that dose only will proceed to the next endpoint in the hierarchy with  $\alpha = 0.025$ . Otherwise, the null hypotheses for both doses will not be rejected, testing will stop, and the next endpoint in the hierarchy cannot be tested.

The first, second, third, and fourth endpoints in the hierarchy are:

- 1. The rate of investigator-confirmed HAE attacks during dosing in the entire 24-week treatment period (Day 1 to Day 168)
- 2. Change from baseline in AE-QoL at Week 24 (total score)
- 3. Number and proportion of days with angioedema symptoms through 24 weeks
- 4. Rate of investigator-confirmed HAE attacks during dosing in the effective treatment period (beginning on Day 8 through 24 weeks)

The process described above will be continued for each endpoint in the hierarchy until either all 4 endpoints have been tested or testing has stopped due to non-rejection of the null hypotheses for both doses for endpoints earlier in the hierarchy. At each level of the hierarchy, the Hochberg step-up procedure is used to control Type I error rates if 2 doses are to be tested. Otherwise, if only 1 dose is being tested, the single test is conducted with  $\alpha = 0.025$ .

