The number and proportion of days with angioedema symptoms through Week 24 will be computed. The proportion of days with angioedema symptoms through Week 24 will be analyzed using an analysis of covariance model with baseline attack rate as a covariate and treatment included as a fixed effect. The estimated treatment difference comparing each active treatment to placebo will be displayed together with the 95% CI and the associated p-value. Least squares means (LSM) will be presented with the standard error and the number of subjects who contribute to the LSM.

For the Investigator-confirmed HAE attacks during the effective treatment period, between-treatment comparisons will be performed using a Poisson regression model similar to that used for the primary endpoint analysis.

A combination of hierarchical testing and the Hochberg step-up procedure will be used to control the Type I error rate for testing of primary and secondary endpoints in Part 1.

Analysis of safety data for Parts 1, 2, and 3 and of effectiveness data for Parts 2 and 3 will primarily be descriptive.

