# 4.3. Sample Size Considerations

# 4.3.1. Sample Size Justifications

The pooled standard deviation (SD) of the attack rate during effective dosing period (Days 8 to 28) in Study BCX7353-203 was 0.55. The observed treatment difference between the BCX7353 125 mg dose with dihydrochloride salt (equivalent to the 110 mg free base dose for the current study) and placebo for the effective dosing period using the full analysis population was 0.70 attacks/week, which represented a 73.8% reduction in attack rate from the placebo group.

Assuming a normalized placebo attack rate of 1 unit and a common SD of 0.55 units for BCX7353 and placebo attack rates, a sample size of 32 subjects will have 94% power to detect a 50% attack rate reduction (a treatment difference of 0.5 units) between BCX7353 and placebo, based on a 2-sided test at significance level of 0.05.

Sample sizes were increased to approximately 40 subjects for each active treatment group and placebo, to conservatively account for a potential dropout rate of 20%. Initial sample size calculations at the time the protocol was written did not allow for dropout.

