### 6.7.5.3. Number and Proportion of Days with Angioedema Symptoms

The number of days with angioedema symptoms is the sum of the days during the reporting period for which at least 1 symptom is reported during an investigator-confirmed HAE attack.

This endpoint will be determined for Parts 1 and 2 as investigator-confirmation will not be calculated for Part 3. As with the calculation of attack rate, if the subject discontinues treatment during the reporting period, any symptoms during confirmed attacks that occur within 24 hours after last dose will be counted in the calculation of days with angioedema symptoms and the additional 24-hour-period will be included in the duration of the reporting period.

The percentage of days with angioedema symptoms is derived as the number of days with angioedema symptoms divided by the duration of the treatment period of interest.

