#### 17. **APPENDIX**

# **17.1.** Table of Contents for Data Display Specifications

Output #	Population	Output Title
14.1.1.1	ITT	Summary of Subject Disposition by Country and Site, Part 1
14.1.1.1.ES	ITT	Summary of Subject Disposition by Country and Site, Entire Study
14.1.2.1	ITT	Summary of Analysis Populations
14.1.2.2	ITT	Summary of Subgroups
14.1.2.3.1	ITT	Summary of Inclusion/Exclusion Criteria Deviations
14.1.2.3.2	Screen Failures	Summary of Inclusion/Exclusion Criteria Deviations
14.1.2.4	ITT	Summary of Protocol Deviations, Part 1
14.1.2.4.ES	ITT	Summary of Protocol Deviations that Occurred During Part 2
14.1.2.5	ITT	Summary of Confirmation of Diagnosis of HAE Type I or II
14.1.3.1.1	ITT	Summary of Demographic Characteristics
14.1.3.1.1.ES	ITT	Summary of Demographic Characteristics - Subjects Who Transitioned to Part 2
14.1.3.1.2	РР	Summary of Demographic Characteristics
14.1.3.1.3	Screen Failures	Summary of Demographic Characteristics
14.1.3.2	ITT	Summary of Subject-Reported HAE Baseline Characteristics - HAE Medical History
14.1.3.3	ITT	Summary of Past Prophylactic Treatments of HAE
14.1.3.4	ITT	Summary of Current On-Demand Treatments of HAE
14.1.3.5	ITT	Summary of Subject-Reported HAE Baseline Characteristics – Primary Acute Attack Treatment Information
14.1.3.6	ITT	Summary of Pre-Treatment Investigator-Confirmed Attack Rates and Angioedema Symptoms
14.1.4.1	ITT	Summary of Medications Taken within 30 Days of Screening and Discontinued Prior to Dosing
14.1.4.2	ITT	Summary of Concomitant Medications, Part 1
14.1.4.2.ES	ITT	Summary of Concomitant Medications – Entire Study
14.1.4.3	ITT	Summary of Concomitant Medications for HAE, Part 1
14.1.4.3.ES	ITT	Summary of Concomitant Medications for HAE, Entire Study
14.1.4.3.P3	ITT	Summary of Concomitant Medications for HAE, Part 3
14.1.4.4	ITT	Summary of Concomitant Medications for HAE – Attack Level, Part 1
14.1.4.4.ES	ITT	Summary of Concomitant Medications for HAE – Attack Level, Entire Study
14.1.4.4.P3	ITT	Summary of Concomitant Medications for HAE – Attack Level, Part 3
14.1.5.1	Safety	Summary of Treatment Exposure and Treatment Compliance, Part 1
14.1.5.1.ES	Safety	Summary of Treatment Exposure and Treatment Compliance, Entire Study
14.2.1.1	ITT	Summary of Hierarchical Testing for Efficacy Endpoints
14.2.1.2.1	ITT	Overall Attack Summary During Part 1
14.2.1.2.1.ES	ITT	Overall Attack Summary During Entire Study
14.2.1.2.2	РР	Overall Attack Summary During Part 1

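### SAP Section 8.5 promises study-level Type I error control, but its single-dose branch lets family-wise error reach about 7% through secondary claims; the primary stays at 5%

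*SAP*

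**What the plan says.** Section 8.5 opens its rule with the claim "The Type I error rate will be controlled at the study level by using a combination of hierarchical testing and the Hochberg procedure". The Statistical methods part of the Technical Summary Report makes the same claim for the Part 1 primary and secondary endpoints: "A combination of hierarchical testing and the Hochberg step-up procedure will be used to control the Type I error rate".

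"There are 4 endpoints being tested", in a fixed order: confirmed attack rate over 24 weeks, AE-QoL change at Week 24, days with angioedema symptoms, and confirmed attack rate from Day 8. Each compares 110 mg and 150 mg with the same placebo arm. At a step where both doses are still in play:

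- if the larger p-value is below 0.05, both doses are rejected and both move on at 0.05;
- if not, but the smaller p-value is below 0.025, that dose alone is rejected and "testing for that dose only will proceed to the next endpoint in the hierarchy";
- if neither holds, testing stops.

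On the lone dose, the section adds "Otherwise, if only 1 dose is being tested, the single test is conducted with" an alpha of 0.025. No truncation, reserved alpha or closed-testing argument is given. Section 15, which lists departures from the protocol, has no entry on multiplicity.

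**The concern.** Hochberg's first step compares the larger p-value with the full 0.05. When one dose has an overwhelming result, whether the other is rejected depends only on its own p-value being below 0.05. The whole 5% is then spent on that second dose. If it fails, no alpha remains at that step, yet the rule hands the winning dose 0.025 for the next endpoint. The same 0.025 is used twice.

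A claim of study-level control has to hold for every combination of true and false null hypotheses. This rule fails when two conditions occur together: one dose truly works on an endpoint where the other is null, and the working dose is null on a later endpoint. A null secondary endpoint on its own does no harm.

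What is at stake is the standing of secondary claims after only one dose passes. Table 14.2.1.1, "Summary of Hierarchical Testing for Efficacy Endpoints", would present them as error-controlled when the rule does not guarantee it.

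**Working it through.** **Inputs.** Thresholds of 0.05 and 0.025 come from Section 8.5, with two-sided tests (Section 8.6.1). The 1:1:1 allocation (Section 4.4.1) gives the two dose-versus-placebo statistics a correlation of 0.5 through the shared placebo arm. The SAP gives no correlation between endpoints, so 0, 0.5 and 0.9 are assumed. For power, Section 4.3.1 gives a difference of 0.5, SD 0.55, n = 32 per arm (raised to 40), and 94% power.

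**The plan's own figures.** The noncentrality is 0.5 / (0.55 × √(2/n)), which is 3.64 at n = 32 and 4.07 at n = 40. The two-sample t-test at 0.05 then has 94.7% power at n = 32, in line with the stated 94%. For the primary endpoint, the error over the two doses is 4.8% when both are null and 5.0% when one works with certainty. The nominal 5% is therefore reproduced for the primary.

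**Worst case for the whole family.** Dose A is certain to be rejected on the primary but is null on AE-QoL; dose B is null on the primary. An error occurs if B's primary p-value is below 0.05, or if it is not and A's AE-QoL p-value is below 0.025.

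- Independent statistics: 0.05 + 0.95 × 0.025 = 0.05 + 0.02375 = 0.07375. The simple upper bound is 0.05 + 0.025 = 0.075.
- Correlated statistics: P(|Z1| > 1.960 or |Z2| > 2.241), where corr(Z1, Z2) = 0.5 × endpoint correlation.

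| Endpoint correlation | corr(Z1, Z2) | Family-wise error |
|---|---|---|
| 0 | 0 | 7.37% |
| 0.5 | 0.25 | 7.27% |
| 0.9 | 0.45 | 7.03% |

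**Simulation of the full written rule** (four endpoints, two doses, shared placebo; 1,000,000 runs per configuration, standard error about 0.02 to 0.03 percentage points). Results are at endpoint correlations 0 / 0.5 / 0.9.

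- AE-QoL route (dose A works on endpoints 1, 3 and 4 but not AE-QoL; dose B null throughout), certain success: 7.4 / 7.3 / 7.0%.
- Dose A at the design effect on the primary rather than certain success: 7.2 / 6.9 / 6.1% at n = 40 and 6.9 / 6.5 / 5.8% at n = 32.
- Both doses null everywhere: 4.8%.
- Both doses certain to succeed on the primary, null on all secondaries: 4.8%.
- One dose works on all four endpoints, the other on none: 5.0%.
- Second dose weakly active on the primary (noncentrality 0.5 to 1): 2.7 to 4.0% if the first dose is certain to succeed, and 2.6 to 3.0% if it is at the design effect.

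**How many configurations are affected.** If each dose may work or not on each endpoint, there are 2^8 = 256 patterns; 140 give 7.0 to 7.4% and 116 stay at or below 5%. This count treats the endpoints as free to differ, which overstates the reach. Endpoint 4 is endpoint 1 without its first seven days, and endpoint 3 counts days on which "at least 1 symptom is reported during an investigator-confirmed HAE attack". If endpoints 1, 3 and 4 move together, 4 of 2^4 = 16 patterns are inflated. All four are forms of the AE-QoL route, and two of them also need the dose that fails on attacks to improve AE-QoL.

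**The case against.** The strongest objection is that the inflated configurations are unlikely. The peak needs one dose with exactly no effect on attacks and another that reduces attacks but does nothing for AE-QoL. Section 4.3.1 cites earlier data at the equivalent of the lower dose, "which represented a 73.8% reduction in attack rate from the placebo group". Once the second dose has even a small true effect on attacks, rejecting it is no longer an error, and the rate falls below 5%. This stands as a statement about likelihood. It does not rescue a claim of study-level control, which must hold without assuming that both doses work. The SAP itself provides a branch for exactly one dose passing, and that branch is where the rule fails.

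A second objection is that the size is modest: at most about 2.4 points, on secondary claims only. The 7.4% also counts rejections in either direction. False claims of benefit alone are about 0.025 + 0.975 × 0.0125 = 3.7% in the independent case, against 2.5%. Both points are correct, but the relative excess is about the same either way.

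Third, the 5.0% for the primary assumes that each test is valid at its nominal level. Section 8.6.1 itself raises over-dispersion in the Poisson model. That is a separate question, and it qualifies every figure here.

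Finally, the supplied protocol is for Study BCX7353-202 and the SAP is for BCX7353-302, so any multiplicity text in the 302 protocol cannot be seen. The SAP specifies its rule completely, however, and nothing in its other sections repairs it.

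**Conclusion.** The concern holds. The rule in Section 8.5 does not have the property claimed for it. Family-wise error over the four endpoints can reach 7.0 to 7.4%, or 5.8 to 7.2% when the working dose has the SAP's design effect on the primary instead of certain success. The inflation arises only when the doses split on an endpoint and the surviving dose is null on a later one, most plausibly at AE-QoL. The primary conclusion is not affected by this fault.

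The figures assume normal test statistics, each test valid at its nominal level, a shared placebo arm with equal allocation, and endpoint correlations between 0 and 0.9. The 7.4% needs no simulation; it follows from the two thresholds.

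**What to change.** Replace the single-dose branch in Section 8.5 with a rule that controls error in every configuration. Any of these would do, and the choice is the sponsor's:

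- **(a) Both doses must pass.** Use Hochberg at 0.05 at each step and move on only if both doses are rejected; otherwise later endpoints are nominal. Cost: no formal secondary claims if only one dose wins.
- **(b) One chain per dose.** Test the four endpoints for each dose at 0.025, and pass that 0.025 to the other dose only once a chain is complete. Cost: a dose's primary test is at 0.025 until the other chain finishes, so power at the design effect falls from 94.7% to 90.7% at n = 32 and from 98.0% to 96.1% at n = 40.
- **(c) Truncated Hochberg.** With truncation 0.5, the larger p-value is tested at (0.5 + 0.5/2) × 0.05 = 0.0375, and a single passing dose carries 0.05 − 0.0375 = 0.0125 forward. Cost: a smaller loss on the primary, but only 0.0125 for a lone dose's secondaries.

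Over the same 256 patterns, the maximum simulated error was 5.03%, 5.03% and 5.02% for (a), (b) and (c), which is 5% within simulation error.

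If the present rule is kept, withdraw the claim of study-level control for the secondary endpoints and say that it covers the primary only. In either case, amend the matching sentence in the Technical Summary Report. If the 302 protocol contains the present rule, a replacement also needs an entry in Section 15. The change should be made before Part 1 unblinding. It needs no new data or patients, whereas a later change to an alpha rule could look driven by the results.

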# 8.6. Analysis of the Primary Efficacy Endpoint

## 8.6.1. Primary Efficacy Analysis

The primary efficacy endpoint for Part 1 of the study is the rate of investigator-confirmed HAE attacks during dosing in the entire 24-week treatment period during Part 1 (Day 1 to first dose of Part 2). The first dose in Part 2 is expected on Day 169. The primary efficacy analysis will be produced using the ITT population. The estimand will be based on data from subjects who are on study treatment and this analysis will not include data post treatment discontinuation.

The number of investigator-confirmed HAE attacks for Part 1 will be analyzed by treatment group using appropriate descriptive statistics for the confirmed attack rate (expressed as attacks/month) based on the 24-week dosing period or until study treatment discontinuation, if applicable. An additional summary of confirmed attack rate by month, including change from baseline attack rate and percentage change from baseline attack rate by month, will be produced. The primary efficacy analysis will be conducted using Part 1 data and the primary efficacy endpoints will be summarized and listed by Part 1 treatment group.

The attack rate and the treatment comparisons between each BCX7353 dose and placebo in the rate of investigator-confirmed HAE attacks during the Part 1 dosing period will be analyzed using a Poisson regression model. The number of investigator-confirmed attacks will be included as the dependent variable, the treatment will be included as a fixed effect, the stratification variable (baseline attack rate) will be included as a covariate and the logarithm of duration on treatment will be included as an offset variable. The estimated rate of attack for each treatment group, the treatment differences expressed as the attack rate ratio (BCX7353 over placebo rate ratio) and their associated 95% confidence intervals (CIs) will be provided from the Poisson regression model. The percentage reduction from placebo will be calculated for each dose as:

Rate reduction = 
$$1 - \text{attack rate ratio} = 1 - \frac{R_A}{R_P}$$

Where  $R_P$  is the estimated attack rate for Placebo treatment and  $R_A$  is the estimated attack rate for Active treatment.

Example SAS pseudo-code for the Poisson regression analysis is as follows:

```
proc genmod data = datasetname;
class trt01p catblatk/param=glm;
model icattacks = trt01p catblatk /dist=poisson link=log offset=logdurtrt;
run;
```

All statistical tests will be 2-sided. Multiplicity adjustments for Part 1 analyses for the 2 dose groups are discussed in Section 8.5 along with handling of testing of multiple endpoints.

The Poisson model assumes that the mean and variance are equal. When the variance in the data is larger than the mean, the model is said to be over-dispersed. Over-dispersion is more likely to be a problem if a significant number of subjects have no attacks during the 24-week treatment period. As a sensitivity analysis to examine the appropriateness of the Poisson model, a negative binomial model will be used in place of the Poisson regression model. When the negative binomial dispersion parameter is equal to zero, the negative binomial and Poisson models are equivalent. If the results of the model obtained using the negative binomial distribution are similar to that of the model that assumes the Poisson distribution and a statistical test of the dispersion parameter does not show that it is significantly greater than zero, the Poisson model will remain as the primary model for analysis.

Plots of mean confirmed attack rate by month and scatter plots of baseline attack rate vs. 24-week attack rate will be produced with a different color for each treatment. Plots of mean attack rate per month will be updated to include the Part 2 data at the end of the study. Adjusted subject-reported attack rate data per month will be plotted separately for Part 3, as Part 3 does not include investigator confirmation of attacks.

